5.3 Study Procedures

5.3.1 Screening/ Visit 1 (Day -45)

Prior to conducting any procedures, written Informed Consent will be obtained from the parent or LAR, and, if appropriate, Informed Assent from the subject. Subjects screening procedures will be performed within 45 days prior Visit 3 and may be done on more than one day. Abnormal results on screening laboratory tests may be repeated at the discretion of the Investigator.

The following procedures will be performed at screening (Visit 1):

- 1. Obtain written informed consent and assent
- 2. Administer R-MOAS scale
- 3. Administer MINI-KID for ADHD diagnosis
- 4. Administer Vitiello Aggression Questionnaire
- 5. Record medical history
- 6. Record demographic information
- 7. Perform physical examination
- 8. Perform 12-lead ECG
- 9. Confirm Inclusion/Exclusion criteria
- 10. Access for subject number
- 11. Collect urine sample for drug screen and urinalysis
- 12. Collect blood for serum pregnancy test (If Visit 1 and Visit 2 occur on the same day then both urine and serum pregnancy tests must be performed)
- 13. Record vital signs (HR, BP, temperature, and RR)
- 14. Record weight, height, BMI
- 15. Collect blood samples for hematology and chemistry
- 16. Collect blood samples for optional PGx testing
- 17. Administer Columbia Suicide Severity Rating Scale (C-SSRS)
- 18. Administer Investigator CGI-S scale
- 19. Record concomitant medications

5.3.2 Baseline/ Visit 2, Day -15

Visit 2 will occur at least 15 days prior to Visit 3 as per the Schedule of Events and Procedures.

- 1. Administer R-MOAS scale
- 2. Collect urine for drug screen and pregnancy test (If Visit 1 and Visit 2 occur on the same day then both urine and serum pregnancy tests must be performed)
- 3. Conduct training for the electronic IA diary
- 4. Distribution of IA diary

- 5. Record Infrequent IA Behaviors
- 6. Record and assess concomitant medications

5.3.3 Visit 3, Day 1

Visit 3 will occur at least 14 days (±2 days) following Visit 2 as per the Schedule of Events and Procedures.

- 1. Administer R-MOAS scale
- 2. Assessment for any clinically significant changes in medical history
- 3. Confirm eligibility to randomize subject
- 4. Assess IA diary compliance/review training as necessary
- 5. Randomize subject
- 6. Collect urine sample for drug screen, urinalysis and pregnancy test
- 7. Record weight, height and BMI
- 8. Record vital signs (HR, BP, temperature, and RR)
- 9. Collect blood samples for hematology and chemistry
- 10. Administer Columbia Suicide Severity Rating Scale (C-SSRS)
- 11. Administer Caregiver and Investigator-completed CGI-S scale
- 12. Administer SNAP-IV, CHQ-PF 28 and SIPA scales
- 13. Administer safety scales (Simpson-Angus, Barnes-Akathisia, AIMS)
- 14. Record adverse events
- 15. Record Infrequent IA Behaviors
- 16. Record concomitant medications
- 17. Dispense SM via I

5.3.4 Visit 4, Day 15

Visit 4 will occur 14 days (±2 days) following Visit 3 according to the Schedule of Visits and Procedures.

- 1. Administer R-MOAS scale
- 2. Review IA diary compliance and provide training as needed
- 3. Record dosing diary compliance and provide training as needed
- 4. Collect urine sample for pregnancy test and drug screen
- 5. Record vital signs (HR, BP, temperature, and RR)
- 6. Administer Columbia Suicide Severity Rating Scale (C-SSRS)
- 7. Administer Caregiver and Investigator-completed CGI-S scale
- 8. Administer Caregiver and Investigator- completed CGI-I scale
- 9. Administer safety scales (Simpson-Angus, Barnes-Akathisia, AIMS)
- 10. Record adverse events
- 11. Record Infrequent IA Behaviors
- 12. Record concomitant medications
- 13. Collect returned SM assess treatment compliance

14. Dispense SM

5.3.5 Visit 5, Day 22

Visit 5 will occur 21 days (±2 days) following Visit 3 according to the Schedule of Visits and Procedures. Refer to Section 5.3.9 for details regarding timing of the dose of SM prior PK sampling.

- 1. Administer R-MOAS scale
- 2. Review IA diary compliance and provide training as needed
- 3. Record dosing diary compliance and provide training as needed
- 4. Collect urine sample for pregnancy test and drug screen
- 5. Record vital signs (HR, BP, temperature, and RR)
- 6. Collect blood for PK analysis
- 7. Administer Columbia Suicide Severity Rating Scale (C-SSRS)
- 8. Administer Caregiver and Investigator-completed CGI-S scale
- 9. Administer Caregiver and Investigator- completed CGI-I scale
- 10. Administer safety scales (Simpson-Angus, Barnes-Akathisia, AIMS)
- 11. Record adverse events
- 12. Record Infrequent IA Behaviors
- 13. Record concomitant medications
- 14. Collect returned SM; assess treatment compliance
- 15. Dispense SM

5.3.6 Visit 6, Day 29

Visit 6 will occur 28 days (±2 days) following Visit 3 according to the Schedule of Visits and Procedures. Refer to Section 5.3.9 for details regarding timing of the dose of SM prior to PK sampling.

- 1. Administer R-MOAS scale
- 2. Review IA diary compliance and provide training as needed
- 3. Record dosing diary compliance and provide training as needed
- 4. Record vital signs (HR, BP, temperature, and RR)
- 5. Record weight, height and BMI
- 6. Collect blood for PK analysis
- 7. Collect urine sample for pregnancy test and drug screen
- 8. Administer Columbia Suicide Severity Rating Scale (C-SSRS)
- 9. Administer Caregiver and Investigator-completed CGI-S scale
- 10. Administer Caregiver and Investigator- completed CGI-I scale
- 11. Administer safety scales (Simpson-Angus, Barnes-Akathisia, AIMS)
- 12. Record adverse events
- 13. Record Infrequent IA Behaviors
- 14. Record concomitant medications

- 15. Collect returned SM; assess treatment compliance
- 16. Dispense SM

5.3.7 Visit 7, Day 36

Visit 7 will occur 7 days (±2 days) following Visit 6 according to the Schedule of Visits and Procedures.

- 1. Administer R-MOAS scale
- 2. Perform physical examination
- 3. Perform 12-lead ECG
- 4. Review IA diary compliance and provide training as needed
- 5. Record dosing diary compliance and provide training as needed
- 6. Collect urine sample for urinalysis, pregnancy test and drug screen
- 7. Record vital signs (HR, BP, temperature, and RR)
- 8. Collect blood samples for hematology and chemistry
- 9. Administer Columbia Suicide Severity Rating Scale (C-SSRS)
- 10. Administer Caregiver and Investigator-completed CGI-S scale
- 11. Administer Caregiver and Investigator-completed CGI-I scale
- 12. Administer SNAP-IV, CHQ-PF 28 and SIPA scales
- 13. Administer safety scales (Simpson-Angus, Barnes-Akathisia, AIMS)
- 14. Record adverse events
- 15. Record Infrequent IA Behaviors
- 16. Record concomitant medications
- 17. Collect returned SM; assess treatment compliance
- 18. Dispense SM (either taper or conversion card based upon the subject's decision about participation in the open-label extension)

5.3.8 Visit 8/ End of the Study, Day 46

Visit 8 will occur 10 days (±1 day) following Visit 7 according to the Schedule of Visits and Procedures. These procedures will be performed for all subjects who complete the Maintenance period and for those who discontinue early. Subjects who discontinue after Visit 4 will be offered a taper kit and return to the study site to complete Visit 8. Any subject, who discontinues between Visit 3 and Visit 4, will be instructed to return to the study site for the final visit, within one week after discontinuation.

- 1. Administer R-MOAS scale
- 2. Record vital signs (HR, BP, temperature, and RR)
- 3. Record height, weight and BMI
- 4. Collect blood for hematology and chemistry
- 5. Collect urine for urinalysis, drug screen and pregnancy test
- 6. Administer Columbia Suicide Severity Rating Scale (C-SSRS)
- 7. Administer safety scales (Simpson-Angus, Barnes-Akathisia, AIMS)

- 8. Record adverse events
- 9. Record concomitant medications
- 10. Collect SM and assess treatment compliance
- 11. Collect Diary
- 12. Complete/Discontinue subject

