The primary efficacy endpoint is the percent change (PCH_T) in the frequency (unweighted score) of IA behaviors per 7 days in the Treatment Phase (titration + maintenance) relative to the Baseline period calculated over the number of days with non-missing IA diary data.

The primary efficacy endpoint PCH_T will be calculated by $PCH_T = 100^*(T - B)/B$, where T and B are IA behavior frequencies per 7 days during the Treatment Phase and Baseline period, respectively. The IA behavior frequency per 7 days is defined as (SUM/DAY) x 7, where SUM is the total of the 15 IA behaviors reported in IA diary, and DAY is the number of days with non-missing IA score in the IA diary during the specified study period.

Key Secondary Efficacy Endpoints:

- 1. Investigator-rated CGI-S scale
- 2. R-MOAS rating scale
- 3. R-MOAS remission rate defined by a score ≤ 10

Additional Secondary Endpoints:

- 1. Investigator-rated CGI-I scale
- 2. Caregiver-rated CGI-I scale
- 3. Caregiver-rated CGI-S scale
- 4. SNAP-IV rating scale
- 5. CHQ-PF28 rating scale
- 6. SIPA rating scale

Additional Secondary Safety and Tolerability Endpoints:

- 1. Incidence of Adverse Events
- 2. Incidence of Extrapyramidal Symptoms (EPS) as assessed by Simpson-Angus Scale Barnes Akathisia Scale, Abnormal Involuntary Movement Scale
- 3. Columbia Suicide Severity Rating Scale (C-SSRS)
- 4. Laboratory Parameters (Hematology, Chemistry, Urinalysis, Insulin and Prolactin)
- 5. Vital signs, Standardized BMI, Physical Examination and ECG (12-lead)
- 6. Infrequent Behaviors Checklist

Exploratory Endpoints:

1. IA Diary Cross-Validation

The data generated from 810P301 and 810P302 pediatric studies during the diary validation process may be used for cross-validation of the IA Diary in adolescents. If the decision is made to proceed with the analysis, the cross-validation plan and results will be provided in a separate stand-alone report.

This document is confidential. It contains proprietary information of Supernus[®] Pharmaceuticals, Inc. Any viewing or disclosure of such information that is not authorized in writing by the Sponsor is strictly prohibited. Such information may be used solely for the purpose of reviewing or performing this study.

2. Population Pharmacokinetics/Pharmacodynamics:

3. Pharmacogenomics (PGx) Testing:

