Molindone hydrochloride is a first-generation mid-potency compound for which the Sponsor has developed an extended release (ER) formulation (SPN-810), administered orally for the treatment of IA in children with ADHD. The immediate-release molindone (Moban®) was approved in 1974 for the management of schizophrenia in adults and adolescents but was discontinued due to commercial reasons by the original manufacturer. Its effects relative to the second-generation antipsychotics (olanzapine and risperidone) were evaluated in a pediatric population with early-onset schizophrenia and schizoaffective disorder in the Treatment of Early-Onset Schizophrenia Spectrum Disorders Study (TEOSS) (McClellan, et al., 2007). Molindone was selected as the first generation antipsychotic based on its favorable safety profile in comparison with the second generation agents. At the average dose of 60 mg/day molindone was shown to be safe and well tolerated (Sikich, et al., 2008). Molindone was not associated with significant increases in weight/BMI in contrast to olanzapine.

CONFIDENTIAL Version 3

Page **36** of **180**

Molindone has been shown to be effective in treating aggressive behavior in children with undersocialized conduct disorder, aggressive type, in an open label and a double-blind study (Greenhill, et al., 1981; Greenhill, et al., 1985).

Results of randomized controlled trials such as TEOSS and other studies has stimulated interest in the potential usefulness of molindone as a weight- and metabolically-neutral D2-receptor antagonist in children with ADHD and comorbid IA. The overall clinical profile of molindone in children makes it an attractive candidate for the treatment of IA in children and adolescents with ADHD, especially with the anticipated benefits of an ER formulation.

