5.2 Schedule of Visits and Procedures

All subjects who are consented are required to follow the protocol procedures regardless of the number of doses of SM taken. The Sponsor, or the Sponsor's designee, must be notified of all deviations from the Schedule of Visits and Procedures (Table 1), and these procedures, if applicable, should be performed at the nearest possible time to the original schedule. Subjects will be instructed to call study site personnel to report any issues or abnormal reactions during the intervals in between study visits and to return to the study site if medical evaluation is needed especially when urgent. Unscheduled visits may be conducted at the discretion of the Investigator throughout all study periods. The medical monitor must be promptly contacted in the event that any clinically significant findings or information is obtained during the unscheduled visit. For emergency and other unscheduled visits to a medical facility other than the study site, medical records will be obtained by the Investigator or qualified designee as source data for study follow-up by the Investigator.

Supernus® Pharmaceuticals, IncCONFIDENTIAL810P503Version 3

Page 51 of 180

Table 1 Schedule of Visits and Procedures

Phase	Pre-Tre	atment	Treatment		Conversion/Taper			
Period	Screening	Baseline	Titra	ation		Maintenance		
VISIT NUMBER	1	2	3	4	5	6	7	8 (EOS)
DAY	-45	-15	1	15	22	29	36	46
	≤45d prior to	≥15d prior to	14d±2d	14d±2d	21d±2d	28d±2d	7d±2d from	10d±1d from
WINDOW (DATS)	Visit 3	Visit 3	from Visit 2	from Visit 3	from Visit 3	from Visit 3	Visit 6	Visit 7
Informed Consent/Assent ^a	Xp							
R-MOAS Scale	Х	Х	Х	Х	Х	X	X	Х
MINI-KID & Vitiello	v							
Aggression Scales	^							
Medical History	Х		Xc					
Demographics	Х						4	
Physical Examination & ECG	v						v	
(12-lead)	~						^	
Inclusion/Exclusion Criteria	Х		Xd					
Randomization			Xp					
Urine Drug Screen	Х	X	Х	Х	X	X	X	Х
Pregnancy Test ^e	X ^f	Х	Х	Х	X	X	X	Х
Diary Training &		V	Vg	×	×	v	×	
Distribution or Evaluation		~	Λ-	~	^	^	~	
Vital Signs ^h	Х		Х	Х	X	X	X	Х
Weight, Height, BMI	Х		Х			X		Х
Hematology/Chemistry/Uri	×		x				v	×
nalysis	^						^	^
PK Blood Sampling ⁱ					X	X		
PGx sampling ^l	Х							

CONFIDENTIAL Version 3

Page 52 of 180

Columbia Suicide Severity	Х		x	x	х	х	x	х
Rating Scale (CSSRS)	X		~	X	X	X	~	~
Caregiver and Investigator	vi		v	v	v	v	v	
CGI-S	A [*]		^	^	^	~	^	
Caregiver and Investigator				v	v	v	v	
CGI-I				^	^	^	^	
SNAP-IV, CHQ-PF28, SIPA			X				Х	

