5.3.9 Pharmacokinetic Blood Sampling

5.4 Treatments

5.4.1 Treatment Administered

Subjects will take up to (6) six molindone hydrochloride extended release tablet (SPN-810) or placebo twice each day (BID) with or without food, in the morning and in the evening, in addition to the stable dose of the optimized ADHD medication. During the conversion phase, subjects will take up to (8) eight molindone hydrochloride extended release tablet (SPN-810) or placebo twice each day (BID).

If dosing starts before noon, the subject should start with the morning dose; if dosing starts after noon, the subject should start with the evening dose. Subjects will be randomized to one of the two treatments at Visit 3 and will be titrated to the final randomized total daily dose (TDD) of 36 mg/day.

- o Treatment 1: Placebo, PO, BID
- Treatment 2: Flexible dose titrated to one of SPN-810 45 mg, or 54 mg, PO, BID

Subjects will remain at the target dose of 36 mg/day or placebo for one week during maintenance. In the second week of maintenance (Visit 5), the treatment dose could be increased in a blinded fashion to 45 mg (TTD) based on Investigator discretion or maintained at

CONFIDENTIAL Version 3

36mg (TDD) or placebo. In the following week (Visit 6), the Investigator will re-assess the dosage: the subject may remain at 36 mg (TDD) or 45 mg (TDD) or matching placebo (depending on the dosage from the previous week) or titrate up to the higher dose of 45 mg or 54 mg (TDD) or placebo. At the same Visit, dose reduction will be allowed in consultation with the Medical Monitor and the Sponsor: the Investigator may adjust the dose based upon tolerability.

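### Weight and BMI are not scheduled at Visit 7, so the planned baseline-to-EOS change describes subjects after taper or conversion, not at the end of randomized treatment

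*Protocol*

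**What the plan says.** **Schedule.** In Table 1 of both documents the row "Weight, Height, BMI" is marked at Visits 1, 3, 6 and 8. The visit lists agree. Protocol 5.3.6 (Visit 6, Day 29) has "Record weight, height and BMI" and 5.3.8 (Visit 8, Day 46) has "Record height, weight and BMI". Protocol 5.3.7 (Visit 7, Day 36) has 18 items, including a physical examination, a 12-lead ECG, hematology and chemistry, but no weight. Its vital-signs item reads "Record vital signs (HR, BP, temperature, and RR", and Table 1 footnote h defines vital signs in the same way, so weight is not implied.

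**Dose steps.** The Synopsis and Protocol 4.2, 4.3.2.2 and 5.4.1 describe one sequence. Subjects stay at 36 mg/day through the first maintenance week and may go to 45 mg at Visit 5. At Visit 6 they may "titrate up to the higher dose of 45 mg or 54 mg (TDD) or placebo". The Table 2 footnote is looser: it allows adjustment to 45 mg or 54 mg over the last two maintenance weeks without tying 54 mg to Visit 6.

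**After Visit 7.** Subjects receive a blinded taper card or, if entering the extension study, a conversion card leading to 36 mg/day SPN-810 (Protocol 4.2, 4.3.3, 4.3.4). Visit 8 follows completion of that phase.

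**Endpoint and analysis.** The Synopsis and Protocol 3.2 list "Vital signs, Standardized BMI, Physical Examination and ECG (12-lead" among the safety endpoints. SAP 7.3 summarises weight, height and BMI by treatment group as absolute value and change from baseline to EOS. Protocol 9.5.5 plans vital-sign changes from baseline to the final visit and descriptive summaries of height, weight and BMI by treatment group. Table 1 labels Visit 8 as EOS.

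**The concern.** Weight is part of the stated case for the drug. Protocol 2.3 says "Molindone was not associated with significant increases in weight/BMI in contrast to olanzapine" and presents molindone as neutral for weight and metabolism. A reader will therefore look for the weight or BMI difference between arms at the end of randomized treatment. The schedule does not collect it, and the value the SAP uses in its place is taken after the randomized regimens have been altered.

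The alteration differs by arm. SPN-810 subjects who leave are tapered down. SPN-810 subjects who convert are brought to 36 mg/day. Placebo subjects who convert are, on the protocol text, being moved toward active drug. If the drug affects weight over such a period, taper in one arm and active drug in the other both tend to shrink the between-arm difference, which is the unwelcome direction for a safety endpoint. The documents give no figure from which to size this.

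There is also a practical mismatch. Visit 7 chemistry includes glucose, insulin, triglycerides and cholesterol, yet no weight is taken that day to read beside them.

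**Working it through.** This is a check of the schedule; the plan states no figure to reproduce. The inputs are the visit timings in Table 1 and Protocol 5.3.5 to 5.3.8:

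- Visit 5: 21 ± 2 days after Visit 3.
- Visit 6: 28 ± 2 days after Visit 3.
- Visit 7: 7 ± 2 days after Visit 6.
- Visit 8: 10 ± 1 days after Visit 7.

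Each interval is the nominal difference, with the range from adding or subtracting the windows:

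| Interval | Nominal (days) | Range (days) | Arithmetic for the range |
|---|---|---|---|
| Visit 3 to Visit 6 (last scheduled weight on the randomized regimen) | 28 | 26 to 30 | 28 − 2; 28 + 2 |
| Visit 3 to Visit 7 (end of Treatment Phase, no weight) | 28 + 7 = 35 | 31 to 39 | 26 + 5; 30 + 9 |
| Visit 6 to Visit 7 (54 mg window under the stepwise text) | 7 | 5 to 9 | 7 − 2; 7 + 2 |
| Visit 7 to Visit 8 (taper or conversion) | 10 | 9 to 11 | 10 − 1; 10 + 1 |
| Visit 6 to Visit 8 (gap between scheduled weights) | 7 + 10 = 17 | 14 to 20 | 5 + 9; 9 + 11 |
| Visit 5 to Visit 6 (longest 45 mg exposure before the Visit 6 weight) | 28 − 21 = 7 | 3 to 11 | 26 − 23; 30 − 19 |

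Setting the weight row against the dose steps:

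1. At Visit 6 weight is item 5 and dispensing is item 16. Under the stepwise text 54 mg can first start at this visit, so the weight precedes it and reflects 36 or 45 mg/day, or placebo.
2. From the first possible 54 mg dose to Visit 7, the number of scheduled weights is zero. At Visit 7 itself it is also zero.
3. The next weight is Visit 8, after taper or conversion. Subjects who discontinue after Visit 4 are also offered a taper kit before Visit 8. Those who stop between Visits 3 and 4 return within one week of stopping (Protocol 5.3.8).
4. With no scheduled Visit 7 weight, the SAP's EOS value for weight and BMI is the Visit 8 value.

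With a Visit 7 weight, the measurement would fall at the end of the Treatment Phase, before any card is started, and after up to 7 (5 to 9) days on 54 mg for subjects who reached it.

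**The case against.** The case on the other side has real content.

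- **Visit 6 already gives a sound comparison.** It is blinded, randomized and on treatment, after nominally 28 of 35 days, with no taper or conversion involved. This stands, and it is why the existing data can still be analysed properly. It does not help while SAP 7.3 points at EOS.
- **Weight on 54 mg is not a target of the trial.** Dose is flexible at the Investigator's discretion, 54 mg subjects are a selected subset, and weight is summarised by treatment group, not by dose. This also stands. The main loss is the end-of-treatment comparison between arms.
- **Other routes exist.** Protocol 6.4.7 lets the Investigator take vital signs at other times, Protocol 5.2 allows unscheduled visits, and Visit 7 includes a physical examination. None of these calls for a weight, so none gives systematic data.
- **The study was halted (SAP 5.1).** A schedule change cannot recover data. This is correct, and the remedy for existing data has to use Visits 6 and 8.

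Three stronger readings are tempting and are not supported. A reader might infer that 7 of 35 days, or 20%, of treatment goes unobserved for weight. Weight is cumulative, so Visit 8 carries any change from that week, mixed with taper or conversion. A reader might infer that at most 7 days on 45 mg are seen; that is the nominal interval, and the windows allow 3 to 11 days. A reader might infer that weight can never be recorded on 54 mg. The documents support only that no measurement is scheduled there under the stepwise text. If the Table 2 footnote permits 54 mg from Visit 5, a Visit 6 weight could follow some 54 mg exposure.

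**Conclusion.** The point holds. No weight, height or BMI is scheduled at the end of randomized treatment, and the planned baseline-to-EOS summary rests on a value taken 10 (±1) days later, after taper or conversion. The 54 mg part is modest, about one week (5 to 9 days) of exposure in a selected subset. The consequence is a mislabelled timepoint for one named safety endpoint, with a usable on-treatment value at Visit 6. It does not affect efficacy.

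The conclusion rests on three assumptions:

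1. *54 mg first starts at Visit 6.* The Synopsis, 4.2, 4.3.2.2 and 5.4.1 say so; the Table 2 footnote does not. The end-of-treatment conclusion does not depend on how these are reconciled.
2. *EOS for weight means Visit 8.* Table 1 labels it so. SAP 7.4 uses the same term for ECG, which Table 1 does not schedule at Visit 8, so the SAP is not strict about it. For weight, a Visit 7 value does not exist under either usage.
3. *Visit 8 follows a completed taper or conversion.* The daily steps are in Protocol Figures 1 and 2, which were not available for this check, so what each converting placebo subject receives, and when, is taken from the text alone.

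**What to change.** **For any restart or reuse of this schedule:** add weight, height and BMI to Visit 7 in Table 1 and Protocol 5.3.7, and name Visit 7 as the on-treatment timepoint in the analysis plan. Add, not move: moving the measurement would lose the Visit 6 value. The cost is one extra measurement at a visit that already includes a physical examination, vital signs and blood sampling.

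**For data already collected:** amend SAP 7.3 to report baseline to Visit 6 as the weight and BMI change on randomized treatment. Label the Visit 8 value as post-taper/conversion, and show it separately for tapered and converted subjects, identifying early terminators who had no taper. This needs no new data; the cost is an SAP edit and a few more table rows. A Visit 7 timepoint should not be written into the SAP for this study, because no scheduled data stand behind it.

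**Text:** the Table 2 footnote and the dosing passages in the Synopsis, 4.2, 4.3.2.2 and 5.4.1 must be reconciled on when 54 mg may first be given. SAP 7.3 and 7.4 should state which visit EOS means for each measurement.
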